### Collateral Research

- Include biomarkers, PK, etc.

Prick end point titration skin tests will be performed in duplicate with five 10-fold dilutions to commercially prepared aeroallergen extracts of Timothy grass or Short Ragweed and up to two additional environmental allergens, along with three concentrations of codeine (10, 30, and 90 mg/ml). Prick skin testing also will be done with a single concentration of histamine (10 mg/ml) and saline and will be administered simultaneously via a standard skin testing lancet. Skin test results will be recorded after 15-20 minutes by outlining wheals with a pen and then transferring the outline to transparent tape placed over the skin test sites. The tape records will be stored in a lab notebook as shown in Figure 4. The area of each wheal will be measured using image analysis software, and the mean area will be calculated as the average of those two measurements. The net wheal area will then be calculated by subtracting the mean of the duplicate negative control sites from the mean of duplicate allergen, codeine, and histamine skin test sites, and all net area values will be converted to net diameters assuming a perfect circle for each net area. The provocation concentration causing a 3 mm net wheal diameter (PC3) will then be calculated from a plot of the net wheal diameter versus the log allergen concentration, similar to previous publications using this technique.

[figure not shown]

Figure 4. Titration skin testing and calculation of the PC3 value.

Changes in PC3 after desensitization versus baseline and versus placebo will be used to determine the degree of desensitization and of cross-desensitization. Codeine PC3 values are predicted to remain unchanged by allergen immunotherapy, as are the histamine positive and diluent negative controls.

Allergen-specific IgE to penicillin was not measurable in serum from any of the volunteers who underwent desensitization to penicillin in our previous study (data not shown), and thus we were unable to determine if clinically-apparent cross-desensitization was contingent on the amount of allergen-specific IgE or to the ratio of allergen-specific to total IgE, as it was for desensitization of human skin mast cells in vitro. To address this in the current study, aeroallergen-sensitive subjects will be recruited, in whom allergen-specific IgE as well as total IgE levels will likely be measurable on the UniCAP platform (ThermoFisher), permitting an analysis of any association between the absolute or relative amount of allergen-specific IgE to either desensitization or cross-desensitization.

Plasma and cells will be prepared from 100 ml of EDTA-anti-coagulated blood samples collected at each of the three visits. Plasma will then be assayed for total IgE, allergen-specific IgE, and tryptase levels using the Immunocap system (Thermo Fisher Scientific, Uppsala, Sweden). The ratio of allergen-specific to total IgE will be calculated for each time point.

To address the response of basophils to desensitization, basophils will be purified from the blood collected at each time point using protocols previously described. Some cells will be used to determine the baseline activation state of the basophils at each time point, as measured by CD63 or CD203c expression on the cell surface (flow cytometry). Other cells from each time point will be activated by incubation with an Fc $\epsilon$ RI cross-linking antibody, with purified allergens (ones used for titration skin tests) or with C5a, activation being measured by CD63 or CD203c expression. To determine if short-term changes in free allergen-specific plasma IgE correlate with the development of desensitization to allergen challenge, IgE levels at each time point will be compared to the above markers of mast cell and basophil activation (PC3 and CD63/203c expression, respectively).

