## Hypothesis

- List the clinical Hypotheses in order of priority:

**Objective I.** We expect to see desensitization of mast cells and basophils to the allergen utilized during SL immunotherapy, but not to G protein receptor-coupled ligands, such as codeine and C5a. Moreover, it will be of interest to explore whether the magnitude of allergen-specific IgE levels in plasma affects the occurrence,

magnitude, or timing of desensitization. For example, it is possible that allergen-specific IgE in the serum serves to block or delay the arrival of allergen at the surface of mast cells, but perhaps not at the surface of circulating basophils. On the other hand, formation of low levels of small IgE:allergen immune complexes in the circulation might facilitate desensitization. Furthermore, whether desensitization reduces the level of free allergen-specific IgE, and such reduced levels of allergen-specific IgE correlates with desensitization, will be of additional interest.

**Objective II:** Based on our in vitro studies, showing allergen cross-desensitization of mast cell in culture, we expect cross-desensitization of mast cells to occur during SL allergen immunotherapy in most subjects, perhaps depending on the relative amount of the IgE against the desensitizing allergen. A similar incidence of cross-desensitization in basophils is expected based on their similar, but not identical, biology compared to mast cells. Learning how to safely cross desensitize may have important clinical utility, e.g., giving clinicians the ability to desensitize with ragweed SL tablets, and then safely begin immunotherapy with a more dangerous allergen, e.g., peanut or insect venom, or to administer a needed drug, e.g., penicillin or ciprofloxacin, to which the patient had been previously sensitized.

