Secondary outcomes will be analyzed by comparing the percent IgE specific for Timothy grass or Short Ragweed, depending on the subject's initial sensitization, with the fold change in PC3 values after treatment for Timothy grass or Short Ragweed (Objective I) or unrelated aeroallergen (Objective II). Comparisons between continuous variables will be performed by calculating Pearson or Spearman coefficients or by regression modeling.

Subgroup analysis may be performed on any of the above measures if deemed necessary. For example, it may be determined that subjects treated with Timothy grass immunotherapy are more likely to display cross-desensitization than those treated with Short Ragweed immunotherapy.

All calculations will be performed using a statistical analyses software package such as SigmaPlot (Systat, San Jose, CA) or SPSS (IBM, Armonk, NY).

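### The IgE biomarker question concerns change within subjects, but the stated comparison is of IgE levels with PC3 and basophil markers at each visit, so it does not answer the question as posed

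*Combined protocol and SAP*

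**What the plan says.** The Hypothesis section, under Objective I, lists as a matter of additional interest "whether desensitization reduces the level of free allergen-specific IgE, and such reduced levels of allergen-specific IgE correlates with desensitization". The Collateral Research section takes this up. It states the purpose as "To determine if short-term changes in free allergen-specific plasma IgE correlate with the development of desensitization to allergen challenge", and the method that follows in the same sentence is that "IgE levels at each time point will be compared to the above markers of mast cell and basophil activation", the markers being "PC3 and CD63/203c expression, respectively".

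Earlier in Collateral Research, desensitization is given an operational meaning: "Changes in PC3 after desensitization versus baseline and versus placebo will be used to determine the degree of desensitization and of cross-desensitization". The section also says that "The ratio of allergen-specific to total IgE will be calculated for each time point".

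The only other IgE analysis is in Statistical Plans: "Secondary outcomes will be analyzed by comparing the percent IgE specific for Timothy grass or Short Ragweed", depending on the subject's sensitization, "with the fold change in PC3 values after treatment for Timothy grass or Short Ragweed (Objective I) or unrelated aeroallergen (Objective II"). The methods offered there are Pearson or Spearman coefficients or regression. No within-subject method and no term for treatment arm is named.

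**The concern.** The question has a change on both sides: a fall in IgE and the development of desensitization. The stated comparison has a level on both sides. A correlation of levels at one visit is driven mainly by how subjects differ from one another, and those differences exist before any tablet is taken and in the placebo arm.

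The sign adds to the problem. If subjects with more specific IgE react at lower allergen concentrations, IgE and PC3 are negatively correlated whatever the treatment does. The hypothesis (IgE falls, PC3 rises) predicts the same sign. A negative correlation at Visit 2 or 3 could then be taken as evidence about mechanism when it reflects only stable differences in sensitization. At stake is the interpretation of an exploratory biomarker result.

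**Working it through.** **1. Does another section supply the missing analysis?** Set side by side:

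| Section | IgE side | Marker side |
|---|---|---|
| Hypothesis, Objective I | reduction | desensitization |
| Collateral Research, purpose | short-term change | development of desensitization |
| Collateral Research, method | level at each visit | PC3, CD63/CD203c at each visit |
| Statistical Plans, secondary outcomes | percent specific IgE, visit not stated | fold change in PC3 |

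The last row asks whether the IgE share predicts response, not whether a change in IgE tracks it. No section relates IgE change to marker change.

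**2. The plan's own figure.** None is given for this comparison. The 15 treated subjects justified in Statistical Plans concern the IgE ratio and cross-desensitization. That figure cannot be reproduced, because neither the SD of the ratio nor the residual SD of log PC3 is stated.

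**3. How often would the level comparison be significant if treatment left IgE unchanged?** From the documents: 15 active and 15 placebo subjects. Assumed: between-subject SD 0.6 log10 for both variables; visit error SD 0.1 (IgE) and 0.25 (PC3) log10; PC3 rise of 0.5 log10 in the active arm; underlying IgE-PC3 correlation ρ from 0 to -0.7; two-sided 5% test. The calculation covers PC3 only, not the basophil markers.

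- Variance of log IgE: 0.36 + 0.01 = 0.37.
- Variance of log PC3 at Visit 1: 0.36 + 0.0625 = 0.4225.
- Variance of log PC3 at follow-up: 0.4225 + 0.5² × ¼ = 0.485.
- Expected correlation at Visit 1: ρ × 0.36/√(0.37 × 0.4225) = 0.911ρ.
- Expected correlation at follow-up: ρ × 0.36/√(0.37 × 0.485) = 0.850ρ.
- Chance of a significant negative result: about Φ(atanh|r| × √27 − 1.96).

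| ρ | Visit 1: r, formula, simulated | Follow-up: r, formula, simulated |
|---|---|---|
| -0.3 | -0.273, 31%, 32% | -0.255, 27%, 29% |
| -0.5 | -0.455, 72%, 73% | -0.425, 65%, 66% |
| -0.7 | -0.637, 97%, 98% | -0.595, 95%, 96% |

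At ρ = 0 the test is significant in about 5% of trials counting both directions, which is the nominal rate. Repeat simulations differ by one or two percentage points. A second noise model, which fixes the observed correlation at 0.3, 0.5 or 0.7 and includes no treatment effect, gives 37%, 83% and 99.5% with 30 subjects.

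**4. Change against change.** Taking differences from Visit 1 removes the stable part. What remains is error variance of 2 × 0.01 = 0.02 for IgE and 2 × 0.0625 = 0.125 for PC3, uncorrelated. The simulated rate is about 5% at every ρ.

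**5. What a change analysis can and cannot see.** Suppose IgE falls by a common 0.2 log10 in the active arm (assumed), with the 0.5 log10 PC3 rise.

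- *IgE change between arms:* SE = √0.02 × √(2/15) = 0.0516, and 0.2/0.0516 = 3.87. The t test detects the fall in about 96% of trials.
- *Change against change, both arms pooled, no arm term:* r = −(0.2 × 0.5 × ¼)/√(0.03 × 0.1875) = −0.025/0.075 = −0.33, significant in about 46%. This reflects the difference between arms, not tracking within individuals.
- *Change against change with arm in the model:* about 5%. The arm term absorbs the shared fall. A correlation within the active arm alone misses it too, because a constant shift drops out.

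No single change correlation therefore answers both parts of the question.

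**6. Power for individual tracking.** For 80% power at two-sided 5%, the required |r| is tanh(2.80/√12) = 0.67 within 15 active subjects, and tanh(2.80/√26) = 0.50 with 30 subjects and an arm term.

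**The case against.** The strongest reply is that the sentence opens by naming changes, that desensitization is defined nearby as change in PC3, and that regression is allowed. IgE at each time point could then simply mean the serial data from which changes are taken. That reading is possible, but no section states it and the stated comparison is of levels. The text should settle it.

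Second, the design carries its own check. Each time point includes Visit 1, and half the subjects take placebo. A stable correlation would show before treatment about as often as afterwards. This stands. A reader might infer that the planned comparison cannot separate natural differences from a treatment effect, or that it would confirm the mechanism even if nobody's IgE changed. The documents do not support either: the data needed to see through the correlation are collected. What is missing is an instruction to use them.

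Third, the IgE-PC3 correlation is assumed. The First visit text in Study Design/Clinical Plan calls the evidence on the related link between wheal size and specific IgE conflicting. This also stands, so the size can only be given as a range that includes no excess.

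A reader might also infer that the plan expects treatment to lower specific IgE, or that a true change would necessarily be hidden. The Hypothesis section leaves the fall in IgE as an open question, and the documents give no figures that would show such masking.

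Finally, this is collateral research in a study designed for feasibility. That limits the weight of the point but does not remove the mismatch.

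**Conclusion.** The point holds as a mismatch between question and method: a question about within-subject change is assigned a comparison of levels, and no other section supplies the missing analysis. That conclusion needs no numerical assumption.

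The size of the risk does. With IgE unaffected by treatment, a correlation in the hypothesized direction would be significant at a follow-up visit in roughly 29% to 96% of trials for an underlying correlation between -0.3 and -0.7, and no more often than chance at zero. The SDs, the PC3 shift and the correlation are all assumptions. The primary PC3 comparisons, and the planned secondary analysis of IgE share against PC3 fold change, are outside this point. It should be corrected, but it does not threaten the trial's main conclusions.

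**What to change.** In Collateral Research, replace the visit-by-visit comparison with two stated analyses for each follow-up visit:

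- **(a) Does treatment lower IgE?** Compare the change from Visit 1 in log10 allergen-specific IgE between the active and placebo arms.
- **(b) Does IgE change track desensitization in individuals?** Relate the within-subject change from Visit 1 in log10 IgE to the change in log10 PC3 and in basophil activation. Report this within the active arm and, using all subjects, with arm in the model. State that the arm-adjusted result tests individual-level tracking only and does not capture a fall in IgE shared by the whole active arm; (a) covers that.

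Report the visit-wise correlations of levels, including Visit 1, as descriptive.

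The cost is wording only, since the same samples and assays are used. The downside is limited power for (b) with 15 subjects per arm, so it is best reported as an estimate with a confidence interval.

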#### **Statistical Plans**

- Include justification for clinical sample size and primary hypothesis testing:

**Sample size consideration:** Data is sparse on the effect of desensitization on threshold doses during percutaneous skin prick testing. Our previous experiments examined a change in PC3 values, but this was after a rapid, escalating-dose desensitization protocol, and no placebo group was included. Therefore, the proposed experiments have been designed to test the feasibility of measuring desensitization after single-dose sublingual immunotherapy using changes in PC3. A size of 15 subjects per group (treatment and control) was selected based on work recommending a sample size of at least 12 per group based on feasibility and precision about the mean and variance. Moreover, this sample size should allow for adequate analysis of a secondary endpoint—the effect of the ratio of specific to total IgE on the degree of cross-desensitization—for which data is available. Based on published values of Timothy grass-specific to total IgE in immunotherapy patients and the degree of cross-desensitization observed in our previous study, a sample size of 15 in the treatment arm should allow us to detect a 10-fold change in PC3 values per one-percent change in allergen-specific to total IgE ratio with 80% power and a 2-sided significance of 5%.

**Data analysis:** The primary outcome for Objective I will be analyzed by comparing the change in PC3 values to Timothy grass or Short Ragweed between the placebo and active treatment groups using parametric (t test, repeated measures ANOVA) or non-parametric (Mann-Whitney, Friedman) tests, as appropriate for the data. Additionally, the proportions of each group showing clinically-significant desensitization to Timothy grass or Short Ragweed pollen, arbitrarily set at a 10-fold increase in PC3, will be compared using Chi square or Fisher's exact test. The primary outcome for Objective II will be analyzed by comparing the change in PC3 values to unrelated aeroallergen between both treatment groups, using the same methods as described above.

Secondary outcomes will be analyzed by comparing the percent IgE specific for Timothy grass or Short Ragweed, depending on the subject's initial sensitization, with the fold change in PC3 values after treatment for Timothy grass or Short Ragweed (Objective I) or unrelated aeroallergen (Objective II). Comparisons between continuous variables will be performed by calculating Pearson or Spearman coefficients or by regression modeling.

Subgroup analysis may be performed on any of the above measures if deemed necessary. For example, it may be determined that subjects treated with Timothy grass immunotherapy are more likely to display cross-desensitization than those treated with Short Ragweed immunotherapy.

All calculations will be performed using a statistical analyses software package such as SigmaPlot (Systat, San Jose, CA) or SPSS (IBM, Armonk, NY).

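### The primary change in PC3 has no stated scale, baseline covariate or primary time point, and its test is left to the data; log10 PC3 with a fixed model would close the gap almost free of cost

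*Combined protocol and SAP*

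**What the plan says.** Statistical Plans (Data analysis) defines the Objective I primary comparison as "comparing the change in PC3 values to Timothy grass or Short Ragweed between the placebo and active treatment groups", to be made "using parametric (t test, repeated measures ANOVA) or non-parametric (Mann-Whitney, Friedman) tests, as appropriate for the data". Objective II is "comparing the change in PC3 values to unrelated aeroallergen between both treatment groups, using the same methods as described above". Collateral Research adds only this: "Changes in PC3 after desensitization versus baseline and versus placebo will be used to determine the degree of desensitization and of cross-desensitization".

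None of these sentences says whether the change is a difference or a ratio. None names the visit at which it is taken, gives a criterion for choosing the test, or places baseline PC3 or the desensitizing allergen in the model.

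Other parts of the plan use ratios. PC3 is "calculated from a plot of the net wheal diameter versus the log allergen concentration", over five dilutions each tenfold apart. The responder cut is "arbitrarily set at a 10-fold increase in PC3". The sample-size paragraph aims to "detect a 10-fold change in PC3 values per one-percent change in allergen-specific to total IgE ratio". The secondary outcomes are expressed as fold change.

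Under Study Design/Clinical Plan, the Protocol paragraph puts follow-up skin testing at weeks one and four, while the Second visit and Third visit paragraphs put it at two weeks and two months. The Protocol paragraph also allows either one or two unrelated allergens per subject, and no rule is given for combining two.

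**The concern.** Three choices that can alter the primary result (scale, test and time point) are open until the data are seen.

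Scale matters most. As an illustration, take two subjects with baseline PC3 of 1 and 100 and a tenfold rise in each. The absolute changes are 10 - 1 = 9 and 1000 - 100 = 900, while both log10 changes are 1.0. On the absolute scale, subjects with high baseline PC3 dominate. The primary comparison also pools Timothy with Short Ragweed, and Objective II pools various unrelated allergens. Under Treatment, the two tablets are labelled in different potency units. If the skin-test extracts differ likewise, absolute changes have no common unit, whereas a fold change has none to reconcile.

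The list of tests is not a set of interchangeable options either. Friedman ranks repeated measurements within subjects. Running it in each arm and comparing the two results is not a test of active against placebo.

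**Working it through.** **Inputs from the documents.** 15 subjects per arm (Treatment); five tenfold dilutions, spanning 4 log10 (Collateral Research); a tenfold responder cut, 1.0 log10 (Statistical Plans). The two-sided 5% level and 80% power are stated for the secondary IgE-ratio endpoint only.

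**The plan's own power figure.** For 80% power at n = 15, the implied correlation is tanh((1.960 + 0.842)/√(15 - 3)) = 0.67 by Fisher's z, or 0.63 by the regression t test on 13 df. With a slope of 1 log10 per percentage point, the residual SD per percentage point of SD in the IgE ratio is √(1 - r²)/r, about 1.1 to 1.2 log10. Neither SD is given, so the figure can be neither confirmed nor refuted. No power figure is given for the primary outcome. At 15 per arm, a t test detects a standardized difference of 1.06 with 80% power.

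**Assumptions for the comparison.** Log-normal PC3, between-subject SD (b) 0.5-1.0 and within-visit SD (w) 0.3-0.5 log10. Choosing the test from the data is modelled as Mann-Whitney when Shapiro-Wilk rejects in either arm; with a true shift and absolute change this selects Mann-Whitney in 97-100% of trials. There were 4,000 simulated trials per scenario (standard error at most 0.8 points). The baseline-to-follow-up correlation is b²/(b² + w²).

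Power (%) at a 3.2-fold shift (0.5 log10), common units:

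| b, w | Correlation | Absolute change, chosen test | log10 change, t test | log10 ANCOVA | ANCOVA minus absolute | ANCOVA minus log10 t |
|---|---|---|---|---|---|---|
| 0.5, 0.3 | 0.74 | 81.5 | 88.5 | 89.9 | +8.4 | +1.4 |
| 0.5, 0.5 | 0.50 | 42.1 | 46.5 | 54.5 | +12.4 | +8.0 |
| 0.8, 0.4 | 0.80 | 51.6 | 63.2 | 65.5 | +13.9 | +2.3 |
| 1.0, 0.3 | 0.92 | 67.4 | 87.6 | 86.2 | +18.8 | -1.4 |
| 1.0, 0.5 | 0.80 | 35.7 | 48.3 | 48.8 | +13.1 | +0.5 |

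At a tenfold shift the gain over absolute change is 0-9 points. Under the null, the data-chosen test rejects in 4.0-4.9% of trials and ANCOVA in 4.4-5.7%.

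**Why the last column is small.** The variance of a log10 change relative to ANCOVA is 2/(1 + correlation): 1.33 at 0.5 and 1.05 at 0.9. After the small-sample cost these are 1.28 and 1.01. At 0.5, 15 per arm with ANCOVA is worth about 15 × 1.28 = 19 per arm on a change score; at 0.9 there is almost no gain. Most of the advantage over absolute change comes from the log scale.

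**Units and the allergen term.** If the Timothy and Ragweed extract units differ by an assumed 1-2 log10, the loss from absolute change at a 3.2-fold shift is 13-25 points. ANCOVA then needs an allergen term. With total SD 0.75, correlation 0.5 and a 3 log10 offset, power is 41% for log10 change, 41% for ANCOVA without the term and 49% with it.

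**Time point.** For a sustained effect, ANCOVA at one visit gives 48-91% power and ANCOVA on the mean of both follow-ups 61-97%. If the effect builds slowly, a single late visit may be better.

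**Objective II.** With assumed unit offsets between unrelated extracts (SD 2 log10), ANCOVA on the per-subject mean gives 61-80%, against 64-82% for a t test on mean log10 fold change.

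**Additive case.** If PC3 changes were additive (SD 30-50% of the mean), log10 ANCOVA against the data-chosen test on absolute change ranges from -9.6 to +5.3 points.

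**Upper bounds for after-the-fact choice.** Taking the smallest p value from t test and Mann-Whitney on both scales gives 7.6-9.3% false positives at one visit and 14-17% over two. Treating two unrelated allergens as separate rows (70% of subjects assumed to have two) gives 8-12%, against about 5% with one mean per subject.

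**The case against.** The strongest reply is that no passage calls the change absolute. The responder cut, the secondary outcomes and the log-concentration plot all point to fold change, and the sample-size paragraph itself uses the word change for a tenfold ratio. On that reading ANCOVA gains little. This stands: the 8-19 points apply only if an absolute change would have been used.

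A reader might infer that the plan ignores baseline. It does not, since a change score subtracts it. What is missing is a baseline covariate.

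A reader might also infer that log10 ANCOVA beats every listed method at no cost. The documents give no PC3 distribution, and assuming log-normality favours the log scale. Repeated measures ANOVA, which is listed, was run on log10 PC3 with a sustained 3.2-fold effect. Its group-by-time test had higher power than single-visit ANCOVA in four of five settings (one within simulation error), for example 91.4% against 86.3%. It was lower in the fifth, 48.6% against 55.0%. So naming a single primary visit can itself cost power.

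Finally, a reader might take the false-positive figures as the trial's error rate. The plan states neither p-value picking nor separate rows. The tablets' units are given but the skin-test extracts' are not, so the unit offset is also an assumption. The sample size rests on a pilot rule, which softens confirmatory arguments. Even so, the plan names primary outcomes and hypothesis tests, and the pre-specification gap remains under every reading.

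**Conclusion.** The point holds as a should-fix matter of pre-specification, with a gain in efficiency whose size depends on what was meant. Scale, baseline covariate, time point and test criterion are absent from both primary analyses, and Friedman does not answer the between-arm question.

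Under the assumed log-normal PC3 and SDs, at a 3.2-fold shift, log10 ANCOVA is worth about 8-19 points of power against absolute change, and more if extract units differ. Against log10 fold change it is worth about -1 to +8 points, and on the plan's own wording this is the likelier comparison. If PC3 changes are additive, it may lose up to 10 points. The documents do not support saying that the primary analysis is underpowered, invalid or subject to a known inflation of type I error. The false-positive figures are upper bounds under assumed practices.

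**What to change.** **Objective I.** Analyse follow-up log10 PC3 by ANCOVA with treatment, baseline log10 PC3 and index allergen (Timothy/Ragweed). Report the geometric mean fold ratio with a 95% CI. Drop Friedman for the between-arm comparison, and name Mann-Whitney on log10 fold change as a sensitivity analysis.

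**Time point.** Reconcile the two sets of visit times under Study Design/Clinical Plan. Then fix in advance either one primary visit or the mean of both follow-ups, according to whether the effect is expected to be sustained or to build slowly.

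**Objective II.** Use one value per subject, the mean log10 fold change over the one or two unrelated allergens tested, and compare it between arms. Add a baseline covariate only if baseline is first centred within each allergen.

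**Values outside the dilution range.** Fix a rule in advance. One option is to set them to the nearest tested concentration, report their number by arm, and add a censored regression as a sensitivity analysis.

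**Cost.** About a paragraph of wording. The two Objective I covariates are already collected and take residual degrees of freedom from 30 - 2 = 28 to 30 - 4 = 26. No extra subjects, visits or assays are needed.
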